8.2 Statistical Analyses

8.2.1 Primary Endpoint Analysis

The primary endpoint is the event rate of MRI-related adverse events through 1 month post-MRI procedure. The clinical acceptance criterion for the rate of MRI-related adverse events is 7%, drawn from historical rates of significant adverse events in DBS studies. The endpoint will be evaluated for each group and will be reported as the percentage of subjects experiencing the events. The clinical acceptance criterion must be satisfied in both groups (leads-only and full system).

The primary analysis will be conducted on subjects who meet all of the following criteria:

• Signed informed consent

- Met the MRI procedure eligibility requirements at the time of the MRI procedure (as per the MRI Procedure Clinician's manual)
- Had a study MRI procedure

Any adverse event will be included in the primary endpoint analysis if it:

- 1. Is classified as being MRI-related (as determined by the CEC), occurs during or after the MRI procedure, and cannot be attributed to any other cause; **and**
- 2. Is classified as being related to the device (implanted or external component) (as determined by the Investigator); **and**
- 3. Meets the criteria for serious adverse event **or** is a non-serious adverse event that is the result of irrecoverable failure of therapy delivery or device communication.

Examples of MRI-related adverse events that will be included in the primary endpoint analysis are:

- Symptomatic intracranial hemorrhage that cannot be attributed to the implant procedure.
- New and permanent neurological symptoms that cannot be attributed to a cause other than the MRI procedure.
- Lack of therapeutic benefit due to damage to the IPG requiring device replacement (e.g., stimulation cannot be turned on following the MRI procedure, stimulation cannot be adjusted following the MRI procedure).

Examples of adverse events that may be reported but will not be included in the primary analysis are:

- Transient, non-serious complications such as sensory or motor disturbance during the MRI procedure that may result from induced currents on leads.
- Sensation of warmth at the IPG that resolves following the MRI procedure.
- Pain around the implanted IPG site that could be related to the implant procedure.

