1.0 INTRODUCTION

This protocol outlines the multicenter, prospective, post-market clinical follow-up (PMCF) plan to support the safety of St Jude Medical Infinity[™] deep brain stimulation (DBS) systems with MR Conditional labeling. The study will be conducted at up to 25 centers in geographies where Infinity DBS systems with MR Conditional labeling are approved including the European Union and the United States, results of which will be submitted to the European Union Notified Body.

The rate of magnetic resonance imaging (MRI) procedure-related adverse events will be used to support the safety of Infinity DBS systems with MR Conditional labeling when used in compliance with the approved requirements. All MRI procedures and the recommended MRI procedural workflow in this clinical investigation should be followed using the DBS MRI Procedure Information Clinican's Manual to ensure patient and device safety during and after the MRI procedure.

This clinical investigation will be conducted in accordance with this clinical investigation plan (CIP). All investigators involved in the conduct of the clinical investigation will be qualified by education, training, or experience to perform their tasks and this training will be documented appropriately.

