3.0 CLINICAL INVESTIGATION DESIGN

This study will be conducted as an international, multicenter, observational, prospective, single-arm, post-market clinical follow-up (PMCF). The study will evaluate the safety of the Infinity DBS system with MR Conditional labeling when an MRI procedure is performed according to the approved guidance. The results of this study will be submitted to the notified body.

The study will be conducted at centers that are qualified to participate and will enroll up to 74 subjects at up to 25 centers in geographies where Infinity DBS systems with MR Conditional labeling are approved including the European Union and the United States. A minimum of 10 centers will be included to ensure a range of MRI equipment brands, including a minimum of 6 in the European Union. Each site will have a maximum enrollment capped at 20% of total enrollment. Subjects who have a leads-only configuration or a full system configuration will participate in the study. Subjects may be enrolled when an MRI procedure is prescribed per standard of care.

Each subject will be limited to one MRI procedure during the course of the study. Selected sites will have this protocol approved to allow for data collection of the MRI parameters and any adverse events (AEs) that occur during the procedure and through 1-month following the procedure. An office visit will be added for all subjects for a 1-month (30 days \pm 14 days) post-MRI follow-up visit after the initial MRI procedure is performed.

The clinical investigation has been designed to involve as little pain, discomfort, fear, and any other foreseeable risk as possible for subjects. Refer to the Risks Analysis section of this clinical investigation plan for details.

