6.0 TREATMENT AND EVALUATION OF ENDPOINTS

6.1 Enrollment

Enrollment and baseline may take place in the same visit. The enrollment visit will take place in the clinic prior to the MRI procedure. The following activities are performed after the subject has been screened and must occur before any procedure/visit.

- The principal or delegated investigator is responsible for screening all potential patients to determine subject eligibility for the study.
- If a patient meets all inclusion criteria and does not meet any of the exclusion criteria, he/she is
 eligible for the study.
- The patient is enrolled in the study after signing the IRB/EC approved consent form.

Record enrollment information (date of consent and inclusion/exclusion information) in the hospital records and complete the enrollment form, preferably within 5 days of enrollment.

As soon as the patient signs the Subject Informed Consent Form, adverse events need to be reported according to the guidelines mentioned in this CIP [section 7.0].

In case the subject was consented to participate in the study, but is later found to not meet inclusion/exclusion criteria, and did not undergo an MRI procedure, the subject should be withdrawn and a withdrawal form must be completed. The subject will resume his/her regular standard of care with his/her physician.

In case the subject was consented to participate in the study and did undergo an MRI procedure, but does not meet inclusion/exclusion criteria, it is considered a protocol deviation. A protocol deviation form needs to be completed and the sponsor must be informed. The subject will be followed through the 1 month visit.

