6.3 MRI Procedure

The MRI procedure will take place at an appropriate facility. The MRI procedure must be performed according to the guidelines outlined in the MRI Procedure Information Clinician's Manual.

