6.3.2 Immediate Post-MRI Procedure (In clinic, after the MRI procedure has been performed)

The following data will be collected after the MRI procedure:

- MRI scanner manufacturer/model
- Scan region (anatomic location)
- Subject position during MRI procedure
- Static field strength
- RF coil type
- RF power
 - o B1+RMS, head SAR, and/or whole body SAR, if applicable
 - Duration of each scan
- Total active scan time
- DICOM image files (de-identified), if available
- Adverse events
- Protocol deviations (if applicable)
- Withdrawal (if applicable)
- Device deficiency (if applicable)
- Product out of service (if applicable)

For subjects in the full system configuration group, the following additional data will be collected immediately after the MRI procedure:

- Success or failure of 'turn off' functionality of MRI mode
- Success or failure to 'turn on/off' functionality of the stimulation
- Success or failure to make adjustments to the stimulation amplitude
- Success or failure of device interrogation and download of IPG parameters Success or failure to obtain lead impedance measurements (only if the Clinician Programmer is being used to interrogate the IPG)

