# 2.13 Sensitivity Analysis

No sensitivity analysis is planned for this clinical investigation.

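### Scanned subjects judged MRI-ineligible leave the primary analysis, and the 7% criterion is never checked with them included

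*Protocol*

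**What the plan says.** **Population.** CIP 8.2.1 opens with "The primary analysis will be conducted on subjects who meet all of the following criteria". It then lists signed consent, a study MRI, and "Met the MRI procedure eligibility requirements at the time of the MRI procedure", the last defined by reference to the manufacturer's MRI manual. SAP 2.3.1 uses a Primary Analysis Population whose definition in SAP 2.1.1 is redacted. SAP 6.0 lists what the SAP adds to the CIP, and no change of population is among the additions. CIP 8.1 gives examples of enrolled subjects left out of the primary analysis, and all of them are subjects who were not scanned.

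**Decision rule.** SAP 2.3.1 passes a group if its observed rate is below 7%. CIP 8.9 and SAP 2.7 require both groups to pass. SAP 2.11 states that no hypothesis is tested. SAP 2.13 reads "No sensitivity analysis is planned for this clinical investigation".

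**Timing of the records.** CIP 6.3.1 and the schedule in CIP 6.4.4 place MRI eligibility before the scan. CIP 6.3.2 collects the scan parameters afterwards: field strength, coil type, scan time and "B1+RMS, head SAR, and/or whole body SAR, if applicable".

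**Question asked.** CIP 3.0 concerns safety "when an MRI procedure is performed according to the approved guidance", and CIP 1.0 concerns the system "when used in compliance with the approved requirements". CIP 6.3 makes adherence to the manual a rule of conduct, not a population criterion.

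**Deviating subjects.** CIP 6.1 treats a subject who was scanned despite failing the study's inclusion or exclusion criteria as a protocol deviation, and adds "The subject will be followed through the 1 month visit".

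**The concern.** A subject recorded as ineligible at the pre-scan check would not normally be scanned. The filter in CIP 8.2.1 therefore has work to do mainly when ineligibility comes to light afterwards. The study is open label (SAP 1.6), so by then the site and the sponsor may know whether an event occurred. The Clinical Events Committee adjudicates relationship to the MRI, but neither document gives it, or anyone unaware of outcome, a say in who belongs to the population.

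If an event prompts a closer look at eligibility, exclusions would fall more often on subjects with events, and the rate in a single-arm safety study would be lowered. The outcome is a bare comparison of an observed proportion with 7% in groups of about 35, so one subject can matter. The data that would show whether it mattered are largely collected already, yet the SAP plans no analysis that puts excluded scanned subjects back and applies the criterion.

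A secondary point concerns the scan itself. The CIP's listed criteria do not ask whether it was run under the labelled conditions, and the SAP names no use for the recorded scan parameters.

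**Working it through.** **Inputs.** About 35 subjects per group, up to 74 enrolled and 5% attrition (CIP 5.8); pass if the rate is below 7% in each group (SAP 2.3.1); rate counted as subjects with an event (CIP 8.2.1). The documents give no expected event rate and no expected number of ineligible scanned subjects. The text of CIP 8.3 and SAP 2.4 on sample size does not appear in the public copies.

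**1. The plan's own figure.** 2 × 35 = 70, and 70/0.95 = 73.7, rounded up to 74. Enrolment is reproduced.

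**2. The pass/fail boundary.** For n = 35: 2/35 = 5.71% passes and 3/35 = 8.57% fails. The largest passing count is 2 for every n from 29 to 42.

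**3. Effect of excluding one scanned subject with a qualifying event** (n = 35 scanned):

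| Events among all scanned | All scanned | After exclusion | Verdict |
|---|---|---|---|
| 2 | 2/35 = 5.71% | 1/34 = 2.94% | pass either way |
| 3 | 3/35 = 8.57% | 2/34 = 5.88% | fail becomes pass |
| 4 | 4/35 = 11.43% | 3/34 = 8.82% | fail either way |

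Only the middle row flips. The same flip occurs for any scanned group of 30 to 42: at the ends, 3/30 = 10.0% becomes 2/29 = 6.90%, and 3/42 = 7.14% becomes 2/41 = 4.88%. It decides the study only if the other group passes.

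**4. Excluding a subject without an event** raises the rate. Near these sizes it changes a verdict only at the edges: 2/29 = 6.90% becomes 2/28 = 7.14%, and 3/43 = 6.98% becomes 3/42 = 7.14%.

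**5. How likely is the flip?** It needs exactly three qualifying subjects. P(X = 3) = C(35,3) p³(1 − p)³², with C(35,3) = 6545 and the true rate p assumed:

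| Assumed p | P(X = 3) |
|---|---|
| 1% | 0.5% |
| 2% | 2.7% |
| 3% | 6.7% |
| 5% | 15.9% |
| 7% | 22.0% |

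Each figure is an upper limit, per group, on the chance of this single-subject flip. It must still be multiplied by the chance that one of the three is classed as ineligible, which cannot be derived from the documents.

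**The case against.** The strongest reply is that the plan already fixes eligibility in time. The criterion refers to the moment of the MRI, the eligibility item is collected beforehand, and CIP 11.0 describes an electronic record with a dated audit trail and reasons for change. This weakens any suggestion that exclusions are free to follow outcomes. What remains is that no sentence makes the pre-scan record decisive or says how later-discovered ineligibility is handled.

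Second, excluded events are not hidden. SAP 3.2 summarises all adverse events in all enrolled subjects with their device and MRI relationship, SAP 3.5 tabulates all MRI-related events, and SAP 3.4 summarises deviations. This stands. What is missing is a comparison with 7%.

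Third, the eligibility filter fits a question about use within the label. This also stands, and it is why the primary set should be kept.

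Two stronger readings are tempting. A reader might infer that the plan keeps scans run outside the labelled conditions. The CIP's list does not exclude them, but the manual is not among the documents and SAP 2.1.1 is redacted, so eligibility as defined there may cover scan conditions. If such scans stay in and carry more risk, they raise the rate and make passing harder. A reader might also infer from CIP 6.1 that every deviating subject is followed for a month and then dropped. That section concerns the study's inclusion and exclusion criteria, which overlap with the manual's MRI eligibility but are not the same. A subject who fails only a study criterion can remain in the primary analysis.

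**Conclusion.** The point holds in a limited form. The primary analysis leaves out scanned subjects who did not meet MRI eligibility. The readable text neither makes the pre-scan record decisive nor keeps later eligibility decisions separate from knowledge of adverse events, and no planned analysis tests the criterion with those subjects included. In a group of 35, one such exclusion turns a fail into a pass only when exactly three scanned subjects have qualifying events. That is improbable at low true rates, and the number of ineligible scanned subjects is not stated.

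The documents do not show that exclusions will depend on outcome, so a claim that the rate is biased downward would go too far. They leave that possibility open where closing it costs little. This is a cheap improvement and does not invalidate the primary analysis. The conclusion assumes that the redacted SAP 2.1.1 does not already settle how eligibility is decided.

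**What to change.** 1. Keep the primary analysis set. State in SAP 2.1.1 that MRI eligibility is taken from the pre-MRI form, and that any later change is made before database lock by someone unaware of the subject's adverse-event outcome.
2. Replace SAP 2.13 with a supportive analysis: for each group, the primary-endpoint rate in all subjects who had a study MRI, set against 7%. List every scanned subject excluded from the primary set, with the reason and event status.
3. Where the recorded parameters allow, add a second row restricted to subjects whose scan met the labelled conditions. The RF measures are collected only where applicable, so report how many scans could not be classified.
4. Align CIP 8.1 with CIP 8.2.1 by naming scanned but MRI-ineligible subjects among those left out of the primary analysis.

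The cost is SAP wording, a one-line clarification in the CIP, two table rows per group, one listing and, for the second row, a derived conformity flag. No new visits or data collection are needed. The downside is that the all-scanned rate may look slightly less favourable than the primary one.

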8.2.2 Secondary Endpoint Analysis

The following secondary endpoints will be analyzed for subjects who undergo an MRI procedure with a full system configuration. The endpoint "Rate of successful ability to obtain lead impedance measurements" will include only those subjects who had their IPG interrogated using the Clinician Programmer. Data (success or failure) for these endpoints will be collected immediately after the MRI procedure.

- Rate of successful MRI mode 'turn on/off' functionality of the MRI mode
- Rate of successful 'turn on/off' functionality for the stimulation
- Rate of successful adjustments to the stimulation amplitude
- Rate of successful interrogation and download of the IPG parameters
- Rate of successful ability to obtain lead impedance measurements

Rates will be reported as the percentage of subjects in which the device functionality could be successfully completed.

8.2.3 Additional Safety Endpoint

The frequency of all MRI-related adverse events will be reported as the number of occurrences of each event and the percentage of subjects experiencing each event, and will be summarized in table format.

8.3 Sample Size Calculation and Assumptions

8.4 Timing of Analysis

Analysis of the primary endpoint and additional endpoints will occur once all subjects have either completed the 1-month follow-up or withdrawn from the study.

8.5 Subgroup Analysis

No subgroup analyses are planned for this clinical investigation.

8.6 Procedures for Accounting for Missing Data

No imputation techniques will be used in this study.

8.7 Planned Interim Analysis

Interim analysis will not be conducted; however the CEC will review and adjudicate events periodically until the study is completed.

8.8 Statistical Criteria for Termination

There are no statistical criteria for termination of this clinical investigation.

8.9 Success Criteria

The clinical investigation is successful if the primary endpoint is met for both the lead-only configuration group and the full DBS system group.

8.10 Labeling Claim

This Post-Market Clinical Follow up (PMCF) supports the safety of the Infinity DBS system with MR Conditional Labeling.

8.11 Deviations from Statistical Plan

Any major changes to the statistical plan will be documented in an amendment to the statistical plan. Less significant changes to the planned analyses will be documented in the final report.

9.0 DIRECT ACCESS TO SOURCE DATA/DOCUMENTS

The investigator/institution will permit direct access to source data/documents for the purpose of performing clinical investigation-related monitoring, audits, IRB/EC review and regulatory inspections.

Subjects providing informed consent are agreeing to allow clinical investigation monitors or regulatory authorities to review, in confidence, any records identifying the subjects in this clinical investigation. This information may be shared with regulatory agencies; however, Sponsor undertakes not to otherwise release the subject's personal and private information.

10.0 QUALITY CONTROL AND QUALITY ASSURANCE

10.1 Selection of Clinical Sites and Investigators

The Sponsor will select investigators qualified by training and experience to participate in the clinical investigation. Sites will be selected based upon review of a recent site assessment, if applicable, and the qualifications of the investigators who will participate in the clinical investigation.

10.2 Clinical Investigation Finances and Agreements

The clinical investigation is fully financed by the Sponsor. The Sponsor will establish written agreements with the sites before patient enrollment.

10.3 CIP Amendments

Approved CIP amendments will be provided to the Investigators by the Sponsor prior to implementing the amendment. The Principal Investigator is responsible for notifying the IRB/EC or equivalent committee of the CIP amendment (administrative changes) or obtaining IRB/EC's approval of the CIP amendment (changes in subject care or safety), according to the instructions provided by the Sponsor with the CIP amendment.

Clinical Investigation Plan

Acknowledgement/approval by the IRB/EC of the CIP amendment must be documented in writing prior to implementation of the CIP amendment. Copies of this documentation must also be provided to the Sponsor.

10.4 Training

10.4.1 Site Training

All Investigators and clinical investigation personnel are required to attend Sponsor training sessions, which may be conducted at an Investigator's meeting, a site initiation visit or other appropriate training sessions. Over-the-phone or self-training may take place as required. Training of Investigators and clinical investigation personnel will include, but is not limited to, the CIP requirements, MR Conditional labeling for the Infinity DBS system, electronic case report form completion and clinical investigation personnel responsibilities. All Investigators and clinical investigation personnel that are trained must sign a training log (or an equivalent) upon completion of the training. Prior to signing the training log, Investigators and clinical investigation personnel must not perform any CIP-related activities that are not considered standard of care at the site.

10.5 Monitoring

Sponsor and/or designee will monitor the clinical investigation over its duration according to the CIP-specific monitoring plan which will include the planned extent of source data verification.

Prior to initiating any procedure, the Sponsor monitor (or delegate) will ensure that the following criteria are met:

- The investigator understands and accepts the obligation to conduct the clinical investigation according to the CIP and applicable regulations, and has signed the Clinical Trial Agreement.
- The Investigator and his/her staff should have sufficient time and facilities to conduct the clinical investigation and should have access to an adequate number of appropriate subjects to conduct the clinical investigation.
- Source documentation (including original medical records) must be available to substantiate proper informed consent procedures, adherence to CIP procedures, adequate reporting and follow-up of adverse events, accuracy of data collected on case report forms, and device information.
- The Investigator/site will permit access to such records. A monitoring visit sign-in log will be maintained at the site. The Investigator will agree to dedicate an adequate amount of time to the monitoring process. The Investigator and/or research coordinator will be available for monitoring visits. It is expected that the Investigator will provide the monitor with a suitable working environment for review of clinical investigation-related documents.

10.6 Deviations from CIP

The Investigator should not deviate from the CIP for any reason except in cases of medical emergencies when the deviation is necessary to protect the rights, safety and well-being of the subject or eliminate an apparent immediate hazard to the subject. In that event, the Investigator will notify Sponsor immediately by phone or in writing.

Clinical Investigation Plan

No waivers for CIP deviations will be granted by the Sponsor. All deviations must be reported to the Sponsor using the Deviation CRF. The occurrence of CIP deviations will be monitored by the Sponsor for evaluation of investigator compliance to the CIP and regulatory requirements and dealt with according to written procedures. Investigators will inform their IRB/EC or equivalent committee of all CIP deviations in accordance with their specific IRB/EC or equivalent committee reporting policies and procedures.

In the event of repeated non-compliance, as determined by the Sponsor, a Sponsor's monitor or company representative will attempt to secure compliance by one or more of the following (and not limited to):

- Visiting the investigator and/or delegate
- Telephoning the investigator and/or delegate
- Corresponding with the investigator and/or delegate

Repeated non-compliance with the signed agreement, the CIP or any other conditions of the clinical investigation may result in further escalation in accordance with the Sponsor's written procedures, including securing compliance or, at its sole discretion, Sponsor may terminate the investigator's participation in the clinical investigation.

